diagnostic assessment. We conservatively estimate that 20% of eligible participants will discontinue the intervention prematurely, but all participants who are randomized will be included in the analysis with an intent to treat analytic approach. For ethical reasons, additional treatment will not be withheld for non responders (defined as CGI-I > 2) or anyone for whom additional intervention is indicated in any intervention condition during the 6 month follow up. Non responders (CGI-I>2) at week 12 will be assisted in finding appropriate care from our existing referral resources. All participants will receive 6 month assessments, but any additional treatment received by non responders will be adjusted for in the analyses.

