9. STATISTICAL CONSIDERATIONS

9.1 General Design Issues

The specific aims and hypotheses are as follows:

Specific Aim 1: Short-term Efficacy of Yoga: Our primary objective is to examine the short-term treatment efficacy of yoga on GAD symptoms. We expect that, at post-treatment, a significantly greater proportion of individuals randomized to receive yoga will be classified as "responders" to treatment (CGI-I ≤ 2) than for individuals who receive SE (Hypothesis 1.1). We further expect

that a greater proportion of individuals receiving CBT for GAD will be classified as "responders" than for those receiving SE (Hypothesis 1.2). Moreover, we predict that the rate of "responders" in individuals receiving yoga will be comparable to those receiving CBT at post-treatment (Hypothesis 1.3).

Specific Aim 2: Long-term Efficacy of Yoga (Exploratory Aim): Our secondary aim is to examine the long-term treatment efficacy of yoga on GAD symptoms. We hypothesize that yoga and CBT will be equally effective at the 6-month follow-up (i.e., the "responder" rate for yoga will not be inferior to that for CBT), and that yoga and CBT will each have higher "responder" rates than SE (Hypothesis 2.1-2.3).

Specific Aim 3: Mediation Analyses. Our tertiary aim is to examine and compare the mechanism of treatment changes in yoga and traditional CBT for GAD. We predict that treatment changes in responder rates during yoga treatment will be mediated via changes in mindfulness and changes in vagal tone (Hypothesis 3.1), whereas changes in CBT will be mediated via changes in maladaptive cognitions (Hypothesis 3.2.). Moderators of "responder rates" will also be examined.

These hypotheses can be tested in a five-year multi-site study to examine the comparative efficacy of yoga, CBT, and stress education, a previously employed control condition, for patients with GAD. Patients with GAD will receive 12-weekly yoga, CBT, or stress education sessions delivered in a group format controlling for attention, time, and group format. Independent evaluators will perform assessments before the 12-session intervention phase, at mid-treatment, after the intervention, and at 6-month follow-up.

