9.2 Sample Size and Randomization

A non-inferiority test is the most direct test of our hypothesis that Yoga will be as effective as CBT for both short-term and long-term outcomes. We will perform a non-inferiority test using response rate (response rate is defined as CGI-I ≤ 2) as the outcome on which to compare CBT and Yoga at posttreatment and at follow-up. Since some attrition may occur, we will use last observation carried forward to insure an intent-to-treat analysis. The non-inferiority margin will be half the difference in response rates between the active comparison (CBT) and placebo. Based on earlier literature, we can expect response rates in our particular CBT and placebo conditions of 57.9% in CBT and 22.2% in placebo. Thus, our non-inferiority margin will be set at ¹/₂ the difference between 56.7 and 22.2, or 17.85%. Using the power analysis program PASS 12, we find that the number of subjects required to obtain .80 power for the non-inferiority test comparing CBT and Yoga is 95 participants in each of the 2 conditions. We verified this number in a 1000 simulation Monte Carlo study using these same parameters. This number is higher than the number proposed in the original grant. Thus, we will increase the N per cell in CBT and Yoga to 95 (22 additional patients per site) to have adequate power for this non-inferiority test. While the original study was budgeted based on a lower number of participants, with careful management of costs we believe we can manage this increase in participants within the full study budget if awarded as proposed.

For the superiority tests (CBT vs. SE and Yoga vs. SE) on the secondary outcomes (which are continuous), we used the MRM power analysis program PinT 2.12. We assumed 25% missing data, and used data from our recent CBT trials (e.g., Stern et al., 2012) to estimate the variances and covariances needed for PinT. PinT indicated greater than .80 power to detect an effect size as small as d=.27, between a small (d=.20) and medium (d=.50) effect size.

We predict that changes in mindfulness will mediate changes in outcome over time for patients in the Yoga condition, and changes in cognitions will mediate changes in CBT. Plus, changes in RSA and cortisol may also mediate changes in outcome across conditions. We further predict that treatment condition will moderate the effect of Time on the mediators ("a" paths).

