To determine if the results of the analyses for Aim 1 are sensitive to the growth curve model, we will perform a secondary analysis, using a simple ANCOVA-type model, to verify the results of our primary growth curve model. Since the outcome is binary (response to treatment), this analysis will be performed using logistic regression, with the following predictors of outcome at post-treatment: baseline severity based on the CGI-S and SIGH-A, and the two dummy variables coding the contrast between SE and the 2 active treatments. This analysis will be performed twice: once as an ITT analysis with missing outcomes imputed as last observation carried forward, and once as a completer analysis.

Per Protocol Secondary Analysis:

As additional secondary analyses, we will repeat our GLMM and MRM analyses using the per protocol sample. We will use these analyses rather than simpler analyses (such as logistic regression or repeated measures ANOVA) because repeating our GLMM and MRMs will allow a more direct comparison to the results for the intent-to-treat sample, allows inclusion of subjects that miss some assessments (other than baseline and post-treatment), allows the modeling of complex covariances between the repeated measures, and it assumes MAR rather than MCAR.

Follow Up Secondary Analyses:

Analyses of outcome at FU (Aim 2) will be considered exploratory since subjects may seek additional treatment during follow-up. These analyses will follow the analyses of outcome at post-treatment, except one additional assessment (FU) will be added to these analyses. Since response during FU may not follow the growth curve of the treatment phase, the growth curve for Aim 2 will be modeled as "piecewise", separately modeling the growth curve during treatment and follow-up. (Analyses of the secondary outcomes at FU will follow the mixed effects ANOVA model described above since these analyses include only 4 total assessments). We will add an additional dummy variable predictor to the analyses for Aim 2, coding whether or not the subject received additional treatment during FU. We will also add the interactions of this "additional treatment" variable with all the other predictors in the analyses to determine if "additional treatment" impacted response to treatment at FU. This analysis will

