allow us to assess the effect of CBT vs. SE and Yoga vs. SE separately for those who received additional treatment and those who did not. A further analysis will compare the rates at which subjects in the 3 conditions seek additional treatment during the FU period.

Secondary Mediation Analysis for Primary Outcome:

We are interested in mediation of our primary outcome: response at post-treatment. Thus, this analysis will include all assessments through and including post-treatment (but not FU). Our mediation analysis includes 2 independent variables (the contrast of Yoga vs. SE and the contrast of CBT vs. SE) and 3 mediators: mindfulness, vagal tone, and maladaptive cognitions. The "a" paths in the mediation analysis will be the effects of each of the 2 independent variables on each of the 3 mediators. These paths will be derived from three MRMs, one for each mediator as the dependent variable. These MRMs will be identical to the models described above with Time centered at post-treatment. Thus, the effect of each contrast (Yoga vs. SE and CBT vs. SE) will be their effect on each mediator at post-treatment. The "b" paths will be derived from the GLMM model (described above) for differences between treatment conditions at post-treatment, with the dependent variable being "response". The 3 mediators will be included in this growth curve model as additional simultaneous predictors of response. The regression coefficients for the mediators in this analysis become the "b" paths in the mediation analysis (the paths from each mediator to outcome). Significance of mediated pathways will be determined using biascorrected bootstrap mediation analysis (e.g., Fritz and MacKinnon, 2007 [137]). We predict that changes in mindfulness will mediate changes in outcome over time for patients in the Yoga condition, and changes in cognitions will mediate changes in CBT. Plus, changes in RSA and cortisol may also mediate changes in outcome across conditions.

Missing Data. Although we will make every effort to reduce missingness, it is inevitable that some data will be missing. We will use pattern mixture modeling (Hedeker & Gibbons, 2006; Enders, 2011 [138-139]) and rerun our analyses coding for various missing data patterns (no missing data, early dropouts, late dropouts, FU dropouts, etc.) to determine both if missingness impacts our findings and how the differences between treatment conditions depend on the missing data pattern.

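### The 6-month Yoga v SE and CBT v SE contrasts (Aim 2) are conditioned on treatment taken after randomisation, and no section names the all-randomised model as the Aim 2 result

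*Combined protocol and SAP*

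**What the plan says.** Section 9.6 (Follow Up Secondary Analyses) begins with the base form of the Aim 2 analysis: "These analyses will follow the analyses of outcome at post-treatment, except one additional assessment (FU) will be added to these analyses". The growth curve becomes piecewise. Two additions follow. The first is "We will add an additional dummy variable predictor to the analyses for Aim 2, coding whether or not the subject received additional treatment" during follow-up. The second is "We will also add the interactions of this 'additional treatment' variable with all the other predictors in the analyses". The stated product is the CBT v SE and Yoga v SE effects "separately for those who received additional treatment and those who did not". A comparison of uptake between the three arms is also planned.

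Section 3 says of the 6-month assessments that "any additional treatment received by non responders will be adjusted for in the analyses". Sections 7 and 8.1 say only that additional treatments will be considered.

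Additional treatment is linked to outcome by design. Section 3: "Non responders (CGI-I>2) at week 12 will be assisted in finding appropriate care from our existing referral resources". Section 7 adds a route for one arm, in that SE non-responders are to be offered CBT or yoga.

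The Aim 2 hypotheses against SE, in section 9.1, are "that yoga and CBT will each have higher 'responder' rates than SE (Hypothesis 2.1-2.3"). Sections 9.1 and 9.6 call Aim 2 exploratory. Section 1.1 describes long-term efficacy as part of the primary aim and does not use that label.

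**The concern.** Section 9.6 takes its tests from the two arm contrasts (Yoga v SE, CBT v SE). With a 0/1 additional-treatment term and full interactions, those two coefficients become effects among participants who took no additional treatment. That group forms after randomisation. Membership depends on week-12 response, and response is expected to differ by arm: the planning rates in section 9.2 are "57.9% in CBT and 22.2% in placebo", so expected non-response is 42.1% v 77.8%. SE participants who stay out of additional treatment are then a more strongly selected group than the corresponding yoga or CBT participants. Adjusting for the variable without interactions, as section 3 can be read, has the same root problem.

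The hypotheses concern responder rates by assigned arm. A contrast within strata of additional treatment, or adjusted for it, answers a different question. A 6-month statement that yoga or CBT does or does not beat SE could therefore come from a comparison shaped by the week-12 outcome. Because the plan does not say which model is reported, the choice could also be made after the results are known.

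**Working it through.** The plan states no figure for the 6-month contrasts against SE, so there is nothing to reproduce. What follows shows direction and range only. It uses raw 6-month proportions, not the planned piecewise mixed model.

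**From the documents.** Week-12 response r = 0.579 for CBT and 0.222 for placebo (section 9.2); arm sizes 95, 95 and 40.

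**Assumed.** Yoga responds as CBT and SE as placebo. At 6 months 80% of week-12 responders still respond, and 15% of non-responders improve unaided. Additional treatment has no benefit (b = 0), so only selection is shown. Uptake is sN in non-responders and sR in responders, the same in each arm unless stated.

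**Formulas, per arm**
- All randomised: 0.80r + (1−r)(0.15 + b·sN)
- No additional treatment: [0.80r(1−sR) + 0.15(1−r)(1−sN)] / [r(1−sR) + (1−r)(1−sN)]
- Additional treatment: [0.80r·sR + (0.15+b)(1−r)sN] / [r·sR + (1−r)sN]
- Adjusted: weighted least squares on the arm-by-additional-treatment cell means, with arm dummies and one additional-treatment main effect

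**Worked case, sN = 50%, sR = 5%**
- All randomised: yoga 0.4632 + 0.0632 = 0.5264; SE 0.1776 + 0.1167 = 0.2943; difference 23.2 points.
- No additional treatment: yoga 0.4716/0.7606 = 0.6201; SE 0.2271/0.5999 = 0.3785; difference 24.2.
- Additional treatment: yoga 0.0547/0.2395 = 0.2286; SE 0.0672/0.4001 = 0.1680; difference 6.1.

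**Yoga v SE difference in points (all randomised: 23.2 in every row)**

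| Uptake, non-responders / responders | No additional treatment | Additional treatment | Adjusted |
|---|---|---|---|
| 20% / 5% | 23.9 | 12.3 | 22.1 |
| 30% / 5% | 24.2 | 9.2 | 20.8 |
| 50% / 5% | 24.2 | 6.1 | 17.5 |
| 70% / 10% | 22.3 | 8.1 | 14.8 |
| 90% / 5% | 12.9 | 3.6 | 6.7 |
| 100% / 0% (limit) | 0 | 0 | 0 |
| 50% / 50% (no selection) | 23.2 | 23.2 | 23.2 |

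A logistic version of the adjusted contrast, standardised to a risk difference, gives 18.4, 15.7 and 7.2 at 50%/5%, 70%/10% and 90%/5%. With b = 0, the ratio of each contrast to the all-randomised difference does not depend on the assumed 80% and 15%.

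**Unequal uptake.** The offer in section 7 makes higher uptake in SE plausible. Take sN = 80% in SE and 40% in yoga, with sR = 5%:
- No additional treatment: yoga 0.4779/0.8027 = 0.5954; SE 0.1921/0.3665 = 0.5240; difference 7.1 against 23.2.
- If both arms respond at 22.2%, the all-randomised difference is 0, but without additional treatment it is 0.2387/0.6777 − 0.1921/0.3665 = 0.3523 − 0.5240 = −17.2 points.
- If both respond at 57.9%, it is 0.5954 − 0.4527/0.6343 = 0.5954 − 0.7137 = −11.8 points.

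**Numbers left.** Of 40 SE participants, those without additional treatment number 40 × 0.5999 = 24, 40 × 0.4332 = 17 and 40 × 0.2887 = 12 at 50%/5%, 70%/10% and 90%/5%.

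**If additional treatment works.** With b = 0.25 at 50%/5%, the all-randomised difference is 0.5790 − 0.3916 = 18.7 points. That fall reflects what happened to participants as randomised; it is not selection bias.

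**The case against.** The strongest reply is that section 9.6 does describe an Aim 2 analysis without the term. It starts from the post-treatment model with follow-up added, and only then introduces the dummy and interactions, with the separate purpose of seeing whether additional treatment affected 6-month response. Sections 8.1 and 9.3 call the analyses intent to treat. The plan also recognises the problem: it keeps follow-up data out of the primary analyses and makes Aim 2 exploratory precisely because participants may seek other treatment.

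The base-model reading is possible, but the text does not settle it. The term is added to the Aim 2 analyses themselves, and nothing says that both models are fitted or which one is reported. The statement that a similar approach can be used at follow-up does not fill that gap. The intent-to-treat statements fix who is analysed, not which variables enter the model. The exploratory label lowers the weight of the result without making the contrasts randomised.

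On size, some of the reply stands. Every uptake figure is assumed. At low, equal uptake the no-additional-treatment and adjusted contrasts barely move, and at 50%/5% and 70%/10% the former moves by only about 1 point. Complete erasure occurs only at the limit where additional treatment coincides with week-12 non-response. The adjusted column corresponds to the wording of section 3, not to the full-interaction model of section 9.6. Against that, the additional-treatment stratum is well below 23.2 in every selective scenario, and unequal uptake can shrink the no-additional-treatment contrast or create a difference between identical arms.

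It is also fair to say that long-term efficacy could be framed under another estimand, since the all-randomised contrast includes SE participants who later take yoga or CBT. That is a reason to state which result leads, and hypotheses about responder rates by assigned arm point to the all-randomised one.

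**Conclusion.** The concern holds. Followed as written, section 9.6 conditions the 6-month Yoga v SE and CBT v SE contrasts on a variable that arises after randomisation and is tied to week-12 non-response. No section names the model without it as the Aim 2 result.

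Under the equal-uptake assumptions, at 50%/5%, 70%/10% and 90%/5%, selection alone moves the 23.2-point difference by about 1, 1 and 10 points in the no-additional-treatment stratum. It lowers it by 15 to 20 points in the additional-treatment stratum and by 6 to 17 points in the adjusted contrast. It vanishes if uptake is unrelated to response. These are illustrations, not estimates from the documents.

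The change should be made, but it is not critical. Aim 2 is exploratory. Aim 1 is untouched, as is the Yoga v CBT non-inferiority test at follow-up, which sections 9.2 and 9.5 describe without this term. Confidence is medium, because the base-model reading cannot be excluded and the real uptake is unknown.

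**What to change.** In section 9.6, state that the main Aim 2 analysis for Yoga v SE and CBT v SE, still exploratory, is the piecewise model in all randomised participants with data, without the additional-treatment term or its interactions. Keep the model with the term as a descriptive supplement, reported beside the planned comparison of uptake by arm, and say that its contrasts are not randomised comparisons. In section 3, replace the statement that additional treatment is adjusted for with one saying that it is described by arm and examined in the supplementary model.

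The cost is wording only. Additional treatments are already monitored, so no new data are needed. The all-randomised difference may turn out smaller than the estimate among those without additional treatment.

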1.2. Secondary Objectives

Specific Aim 3: Mediation Analyses. Our tertiary aim is to examine and compare the mechanism of treatment changes in yoga and traditional CBT for GAD. We predict that treatment changes in responder rates during yoga treatment will be mediated via changes in mindfulness and changes in vagal tone (Hypothesis 3.1), whereas changes in CBT will be mediated via changes in maladaptive cognitions (Hypothesis 3.2.). Moderators of "responder rates" will also be examined.

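### Aim 3 promises to compare how yoga and CBT work, but the mediation analysis tests each only against stress education and specifies no yoga-versus-CBT contrast of indirect effects

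*Combined protocol and SAP*

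**What the plan says.** The objective is comparative. Section 9.1 states: "Our tertiary aim is to examine and compare the mechanism of treatment changes in yoga and traditional CBT for GAD". The Précis and section 1.2 say the same, and the theoretical-innovation paragraph in section 2.2 presents a direct yoga–CBT comparison as the way to learn about mechanism. Hypothesis 3.1 names mindfulness and vagal tone for yoga; the sentence then turns to CBT, "whereas changes in CBT will be mediated via changes in maladaptive cognitions (Hypothesis 3.2").

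The analysis is in section 9.6, under the secondary mediation analysis for the primary outcome:

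- Contrasts: "Our mediation analysis includes 2 independent variables (the contrast of Yoga vs. SE and the contrast of CBT vs. SE) and 3 mediators". The mediators are mindfulness, vagal tone and maladaptive cognitions.
- The a paths: "paths in the mediation analysis will be the effects of each of the 2 independent variables on each of the 3 mediators". That makes six, all against SE.
- The b paths: "The 3 mediators will be included in this growth curve model as additional simultaneous predictors of response". There is one coefficient per mediator, common to all arms.
- The test: "Significance of mediated pathways will be determined using biascorrected bootstrap mediation analysis".

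Section 9.2 adds a prediction, "We further predict that treatment condition will moderate the effect of Time on the mediators", and reports power above .81 for a mediated pathway. That figure assumes large a paths for both yoga and CBT against SE and a medium relation of each mediator to response.

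**The concern.** Testing yoga against SE and CBT against SE shows whether each treatment has an indirect effect. It does not show whether the two indirect effects differ, and that is what a comparison of mechanisms needs. With no planned contrast between them, the natural fallback is to set the two verdicts side by side, and a difference in significance is not a significant difference.

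At stake is the interpretation of Aim 3. A mechanism could be reported as particular to one treatment when both move the mediator equally. A real difference could also be missed because both treatments clear the bar against SE.

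**Working it through.** **Inputs from the documents.** Arm sizes are 95 yoga, 95 CBT and 40 SE (Précis, section 3). The assumed placebo response is 22.2% (section 9.2), used here for SE. The a paths are called large and the b paths medium, without numbers.

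**Assumptions made here.** Two-sided 0.05; mediator SD 1; large a = 0.8 SD and medium a = 0.5 SD; b between 0.42 and 0.91 log odds per SD; independent patients; no dropout.

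**1. The plan's own power figure.** A simplified cross-sectional version (three mediators, bias-corrected bootstrap, 400 samples of 1,000 resamples) with a = 0.8 in both arms gives power 81.5% at b = 0.42 and 91% at b = 0.5. A smaller run gives about 99% at b = 0.91. The stated figure of above .81 is consistent with these. It cannot be strictly reproduced, because the documents give no alpha and no numeric effect sizes. It concerns a single pathway, not a difference between pathways.

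**2. Precision of the contrasts.**

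- Against SE: √(1/95 + 1/40) = 0.188 SD.
- Yoga against CBT: √(2/95) = 0.145 SD.
- Correlation of the two contrasts with SE: (1/40) / (1/95 + 1/40) = 0.70.

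**3. How often the two verdicts split when yoga and CBT act identically.** Take b as certain to be detected. With δ = a/0.188 − 1.96, each pathway is significant with probability p = Φ(δ), and both are with probability Φ₂(δ, δ; 0.70). The split rate is 2(p − Φ₂).

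| True a, both arms | p | Both significant | Split by formula | Split in simulation (b = 0.5 and 0.8) |
|---|---|---|---|---|
| 0.3 | 0.356 | 0.239 | 23% | 21–23% |
| 0.4 | 0.564 | 0.440 | 25% | 23–25% |
| 0.5 | 0.756 | 0.658 | 20% | 18–20% |
| 0.6 | 0.889 | 0.832 | 11% | 10–12% |
| 0.8 | 0.989 | 0.981 | 2% | 1–2% |

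The simulation column requires both the a and the b path to be significant (2,000 trials per setting). The planned bias-corrected bootstrap gives 18.5–20% at a = 0.5 and 1.5–2% at a = 0.8. Treating the two tests as independent would give 2 × 0.81 × 0.19 = 31%, which is too high: the shared SE arm and the shared b make the tests tend to agree.

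**4. The direct test, (a_yoga − a_CBT) × b.** With identical effects it is significant in 4–6% of trials by joint significance, and in 5–8% with the bias-corrected bootstrap.

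- True a of 0.8 vs 0.3: the a path alone allows at most Φ(0.5/0.145 − 1.96) = 0.93. Allowing for b, power is about 0.84 at b = 0.5 and 0.93 at b = 0.8. The split pattern appears in only 57–63% of the same trials.
- True a of 0.8 vs 0.5: the a path alone allows Φ(0.3/0.145 − 1.96) = 0.54. Allowing for b, power is about 0.5.

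**The case against.** A reader might infer that the plan intends to declare that a mediator works for yoga and not for CBT by comparing significance labels. The documents do not support that. No such statement or rule appears, so the supportable point is that the comparison is unspecified.

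A reader might also take Hypotheses 3.1 and 3.2 as claims of exclusivity. Each says what mediates one treatment; neither says the mediator is inactive in the other. Sections 9.2 and 9.6 allow RSA, the plan's measure of vagal tone, to mediate across conditions. For the hypotheses taken singly, the tests against SE are the right ones. This stands.

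The missing contrast is also nearly present. Section 9.2 predicts moderation of the a paths by condition. Section 9.6 says its categorical-time coding yields all contrasts between conditions. With b shared, the arms can differ only through a, and the yoga–CBT contrast is a linear combination of fitted terms. That makes it derivable, not prespecified: neither passage names a yoga–CBT test of mediation.

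Finally, the plan's planning case is large a paths, where splits occur in about 2% of trials, below the direct test's own false-positive rate. If a mediator moved by 0.8 SD in one arm and not at all in the other, the split pattern would appear in about 95% of trials (b = 0.91). So the risk of false splits is not high everywhere. But if both treatments move every mediator strongly, nearly all pathways are significant and the tests against SE cannot show specificity at all.

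**Conclusion.** The gap is real. Aim 3 promises a comparison of yoga and CBT mechanisms, and the one mediation analysis contains no test of it. If the results were read by comparing significance labels, identical treatments would appear to differ in about 19–25% of trials at a = 0.3 to 0.5 SD and about 2% at 0.8 SD. The last is the value assumed here for the plan's large a paths.

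These figures rest on the assumptions listed above and ignore the planned three-level clustering and repeated measures, so they indicate scale only. Aim 3 is tertiary and the mediation analysis is labelled secondary, so no primary conclusion changes. This is a cheap improvement.

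**What to change.** Add one paragraph to section 9.6 before any unblinded analysis:

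1. In the same bootstrap, report (a_yoga − a_CBT) × b with its interval for each of the three mediators.
2. Claim that a mechanism is specific to, or stronger in, one treatment only where that interval excludes zero.
3. Keep the tests against SE for Hypotheses 3.1 and 3.2 as they are.
4. State the limited power of the difference and that a null result is not evidence of equal mechanisms.

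The cost is that paragraph: the data, models and resamples are unchanged. The downside is that some claims of a specific mechanism may no longer be supportable. The contrast should be fixed in advance, because adding it after seeing a split would be post hoc.
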